8.3.4 Adverse Event Reporting

Adverse events will be graded according to the DAIDS Table for Grading the Severity of Adult and Pediatric Adverse Events (DAIDS AE Grading Table), corrected Version 2.1, July 2017, on the DAIDS RSC website at <http://rsc.tech-res.com/clinical-research-sites/safety-reporting/daids-grading-tables>.

The study will monitor participants for adverse events. Toxicities will be characterized in terms including duration, intensity, and time to onset. Safety endpoints will include all adverse experiences, in addition to laboratory safety assessments, and vital signs. All AEs will be recorded on the appropriate study form.

AEs will be recorded in the database if any of the following criteria have been met:

- Study-related Grade ≥ 1 AEs
- Grade ≥ 3 AEs
- Autoimmune-related AEs regardless of grade
- HIV viral loads ≥ 50 copies/mL
- Injection reactions regardless of grade
- AEs that led to a change in study intervention regardless of grade
- AEs meeting SAE definition or EAE (Expedited Adverse Event) reporting requirement

Grade 1 or 2 Toxicity

Participants who develop a Grade 1 or 2 AE or lab toxicity that occurs following a vaccine/placebo injection that is thought to be possibly, probably, or definitely related to the study treatment should be discussed with the study team. Grade 1 or 2 AEs that may be related to the vaccine/placebo injection will be handled according to standard clinical practice and documented.

Grade 3 Toxicity

For participants who develop a Grade 3 AE following the administration of vaccine/placebo judged by the study PI (or designee) to be at least possibly study treatment-related, the protocol team must be notified within 24 hours. Participants experiencing Grade 3 AEs should be followed closely and if the AE does not return to

Grade ≤ 2 within 2 weeks, the study team should again be notified within 24 hours and the SMC will be notified.

For participants who experience a Grade 3 AE judged not related to the study treatment by the investigator, continued study participation is at the discretion of the study PI (or designee) in consultation with the protocol team and SMC.

Grade 4 Toxicity

For participants who develop a Grade 4 AE following administration of vaccine/placebo judged by the study PI (or designee) to be at least possibly study treatment-related, the protocol team and SMC must be notified within 24 hours. Participants experiencing Grade 4 AEs should be followed closely with additional clinical assessments and laboratory testing as clinically indicated. If the AE does not return to Grade ≤ 2 within 2 weeks, the protocol team and SMC should again be notified within 24 hours.

All study treatments will be discontinued in the event of Grade 4 AEs possibly related to study treatment.

Local or Systemic Reactions to Vaccine/Placebo Injections

Grade 1 or 2

Local reactions of mild (Grade 1) or moderate (Grade 2) severity will usually resolve spontaneously. If needed, they may be managed with local application of cold packs, oral acetaminophen, oral non-steroidal anti-inflammatory agents, or a combination of these measures as appropriate.

NOTE: Topical steroids should not be applied to the injection site.

Grade 3 or 4

For severe (Grade 3) or potentially life-threatening (Grade 4) local reactions, the protocol team must be notified within 24 hours. For Grade 4 local reactions, definitive medical and/or surgical intervention should be undertaken as appropriate.

Systemic Reactions

The protocol team must be contacted within 24 hours for any non-local Grade 3 or 4 systemic reactions thought definitely, possibly, or probably related to the vaccine/placebo injections.

The common systemic adverse events usually seen with MVA vectored vaccines, **M3** and **M4**, include headache, feverishness, myalgia, arthralgia, fatigue, malaise, nausea, transient

flu like illness within 24 hours of vaccination, which usually resolves within 48 hours. It is anticipated that the majority of systemic adverse events post vaccination will be mild in intensity. However, there is a possibility of moderate or severe headache or malaise.

If an adverse event of special interest (AESI) occurs (see section 8.3.8), the study coordinator, in collaboration with the study PI (or designee), will evaluate the severity and seriousness of the AE and the relationship to the study treatment, and will document the findings. The protocol team should be contacted within 24 hours of notification of any reactions thought definitely, possibly, or probably related to the vaccine/placebo injections.

Injection Site Reaction

Injection Site Erythema or Redness and Injection Site Induration or Swelling will not be considered an AE if there is no interference with usual social and functional activities such that:

- Grade 1 is: 2.5 to < 5 cm in diameter OR 6.25 to < 25 cm² surface area;
- Grade 2 is: ≥ 5 to < 10 cm in diameter OR ≥ 25 to < 100 cm² surface area;
- Grade 3 is: ≥ 10 cm in diameter OR ≥ 100 cm² surface area OR Ulceration OR Secondary infection OR Sterile abscess OR Drainage;
- Grade 4 is: Potentially life-threatening consequences (e.g., abscess, exfoliative dermatitis, necrosis involving dermis or deeper tissue)

Allergic or Hypersensitivity Reactions

Record all allergic and hypersensitivity reactions with both grade severity and attribution. Serious allergic or hypersensitivity reactions (≥ Grade 3) that are deemed possibly related to the study treatment by the study PI (or designee) will be reported to the protocol team and SMC within 24 hours of notification and to the NIH/DAIDS, UNC IRB, FDA, and study product sponsors within 48 hours per their reporting requirements.

Dose Limiting Toxicity (DLT)

- Hematologic dose-limiting toxicity will be defined as any confirmed toxicity ≥ Grade 2, that cannot clearly be attributed to another reversible cause.
- Follow participants per protocol schedule of events until the lab abnormality or toxicity resolves to ≤ Grade 1 or the participant's baseline.

- Non-hematologic dose-limiting toxicity will be defined as any confirmed symptomatic \geq Grade 3, if related (definitely, probably, or possibly) to vaccine/placebo.

Monitoring HIV RNA levels

In the event of viremia of \geq 50 copies/mL the following should occur per standard of care:

- Adherence to ART should be carefully assessed and documented.
- A standard HIV RNA assay should be repeated within 1-4 weeks.
- HIV resistance testing will be performed at the time of drawing a confirmatory sample and as indicated for persistent viremia.
- For HIV RNA confirmed >200 copies/mL on repeat testing, stored samples may be tested for the presence of one or more ARV drugs in the participant's regimen.
- HIV RNA will be repeated every 2 weeks, or sooner as clinically indicated, until <50 copies/mL and the participant can continue on study.
- In the event of confirmed viremia and documented adherence to ART, ART should be managed by the primary care provider in discussion with the study team. The results of the HIV resistance tests will be shared with the participants and their care providers.

The Protocol Core Team will monitor the conduct and safety of the study via monthly meetings and regular summaries. Accrual, baseline characteristics, conduct of the study (including premature study discontinuations), any interruptions of ART, virologic failures, and all reported toxicities and events will be monitored during the study and discussed with the protocol team on a monthly basis or more frequently, if needed.

The study protocol team will review the individual safety data monthly to assess relation of all reported toxicities and AEs to the study treatment. A study unique independent Safety Monitoring Committee (SMC) will receive monthly study progress and safety monitoring reports. Study feasibility and the achievement of study milestones will be assessed in these reports.

The DAIDS program and medical officers will review and assess the monthly safety reports, as well as EAE reports for potential impact on the study participant safety and protocol conduct as per DAIDS policies, guidance documents, and SOPs, as applicable.

8.3.5 *Serious Adverse Event Reporting*

All SAEs at least probably related to **M3** or **M4** will be considered unexpected and be reported as SUSARs within the regulatory timelines.

All SAEs occurring during the study must be reported to the UNC IRB per the UNC IRB reporting requirements. A written report (Serious Adverse Event Report Form) will be submitted to DAIDS and DAIDS MO within 24 hours of site becoming aware of the SAE. Additional information will be supplied as requested. All SAEs occurring during the study will be reported to DAIDS following guidelines for expedited AE reporting and to the FDA according to their regulatory guidelines.

After 30 days following the last dose of vaccine/placebo, only SAEs the study PI (or designee) considers related to study product or a protocol procedure, should be reported. Information regarding SAEs will be submitted to the DAIDS on required SAE reporting forms, which must be completed and signed by the study PI or designee, and sent within 24 hours of the site becoming aware of the SAE.

All Grade 3 or Grade 4 AE/SAEs considered related to study product must be followed until recovery to baseline or Grade 1 with the date of resolution recorded in the source documents. In addition, the investigator should report all follow-up for reportable Grade 3 or Grade 4 AE/SAEs to the UNC IRB. Resolution of an event is defined as the return to pre-treatment status or stabilization of the condition with the expectation that it will remain chronic.

All SAEs that have not resolved by the end of the study, or that have not resolved upon discontinuation of the participant's participation in the study, must be followed until any of the following occurs:

- The event resolves
- The event stabilizes
- The event returns to baseline, if a baseline value/status is available
- The event can be attributed to etiology other than the vaccine/placebo or to factors unrelated to study conduct
- It becomes unlikely that any additional information can be obtained (participant's or health care practitioner's refusal to provide additional information, or lost to follow-up after demonstration of due diligence with follow-up efforts)

Any event requiring hospitalization (or prolongation of hospitalization) that occurs during the course of a participant's participation in a study must be reported as an SAE, except hospitalizations for the following:

- Hospitalizations not intended to treat an acute illness or adverse event (e.g., social reasons such as pending placement in long-term facility)
- Surgery or procedure planned before entry into the study (must be documented in the source document)

The study PI (or designee) will be responsible for notifying the UNC IRB, FDA, the University of Oxford, and DAIDS of any unexpected fatal or life-threatening suspected adverse reaction as soon as possible, but in no case later than 7 calendar days after the sponsor's initial receipt of the information. In addition, the sponsor must notify FDA in an IND safety report of potential serious risks, from clinical trials or any other source, as soon as possible, but in no case later than 15 calendar days.

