Greenough (57)	MVA.envgag MVA.tatrevnef- RT	HIV	20	IM	5×10^7	2	2	Classified possibly but probably not related to vaccination. Multiple cutaneous bullous lesions, none at immunization sites (developed from a papular lesion at time of immunization) Grade 4 CPK elevation (unexplained CPK elevations occurred prior to study participation)
Dorrell (58)	MVA. HIVA	HIV	16	ID	5×10^7	2	0	None
Cosma (59)	MVA. HIVnef	HIV	10	SC	5×10^8	3	0	None
Harrer (60)	MVA. HIVnef	HIV	50	IM	1 or 5×10^8	3	0	None
TOTAL			126			2		

¹ClinicalTrials.gov NCT02616874

²ClinicalTrials.gov NCT02336074

³ClinicalTrials.gov NCT01712425

⁴ClinicalTrials.gov NCT00189930

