7 STUDY INTERVENTION DISCONTINUATION AND PARTICIPANT DISCONTINUATION/WITHDRAWAL

7.1 Discontinuation of Study Intervention

Premature Treatment Discontinuation Evaluations

There is only one study treatment intervention visit at Day 0. The collection of safety labs, virologic, immunologic, SCA, and the 2nd leukapheresis will continue to be collected per SOE, section 1.3.

Participants who complete the vaccine/placebo injection but do not complete the Day 7 study visit will be replaced, provided the inability to complete the Day 7 visit is not due to a study-related AE.

Participants who complete the vaccine/placebo injection but do not complete the Day 28 study visit and 2nd leukapheresis procedure will be replaced, provided the inability to complete the Day 28 visit is not due to a study-related AE.

Participants who receive vaccine/placebo but are unable to complete the Day 7 or 2nd leukapheresis should be encouraged to continue on study for safety assessments per the SOE.

Discontinuation of Antiretroviral Therapy

If the participant discontinues ART prior to DAY 0, DO NOT give the vaccine/placebo injection. DO NOT collect research labs for the time points after the participant discontinued ART. This participant will be replaced.

If the participant discontinues ART after the vaccine or placebo administration (Day 0), the participant should continue on study for safety follow-up as noted in the SOE. Collection of virologic, immunologic, SCA, and the 2nd leukapheresis samples will be determined on a case-by-case basis in discussion with the protocol team. This participant may be replaced.

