8.3 Adverse Events and Serious Adverse Events

8.3.1 *Definition of Adverse Events (AE)*

Adverse event means any untoward medical occurrence associated with the use of an intervention in humans, whether or not considered intervention-related (21 CFR 312.32 (a)).

An adverse event can therefore be any unfavorable and unintended sign (including an abnormal laboratory finding, for example), symptom, or disease temporally associated with the use of a medicinal product, whether or not considered related to the medicinal product. This includes any occurrence that is new in onset or aggravated in severity or frequency from the baseline condition, or abnormal results of diagnostic procedures, including laboratory test abnormalities.

Definition of Serious Adverse Events (SAE)

An adverse event (AE) or suspected adverse reaction is considered "serious" if, in the view of either the investigator or sponsor, it results in any of the following outcomes:

- death,
- a life-threatening adverse event,
- inpatient hospitalization or prolongation of existing hospitalization,
- a persistent or significant incapacity or substantial disruption of the ability to conduct normal life functions, or
- a congenital anomaly/birth defect.

Important medical events that may not result in death, be life-threatening, or require hospitalization may be considered serious when, based upon appropriate medical judgment, they may jeopardize the participant and may require medical or surgical intervention to prevent one of the outcomes listed in this definition. Examples of such medical events include allergic bronchospasm requiring intensive treatment in an emergency room or at home, blood dyscrasias, or convulsions that do not result in inpatient hospitalization, or the development of drug dependency or drug abuse.

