8.3.2 Classification of an Adverse Event

8.3.2.1 Severity of Event

Event severity will be assigned according to the Investigator's (or designee's) assessment.

Severity Grade for Parameters Not Identified in the Grading Table:

The functional table (

Table 12) should be used to grade the severity of an AE that is not specifically identified in the grading table. In addition, all deaths related to an AE are to be classified as Grade 5.

Table 12 Severity Grade for Parameters

PARAMETER	GRADE 1 MILD	GRADE 2 MODERATE	GRADE 3 SEVERE	GRADE 4 POTENTIALLY LIFE-THREATENING

Clinical adverse event NOT identified elsewhere in the grading table	Mild symptoms causing no or minimal interference with usual social & functional activities with intervention not indicated	Moderate symptoms causing greater than minimal interference with usual social & functional activities with intervention indicated	Severe symptoms causing inability to perform usual social & functional activities with intervention or hospitalization indicated	Potentially life-threatening symptoms causing inability to perform basic self-care functions with intervention indicated to prevent permanent impairment, persistent disability, or death
--	--	---	--	---

8.3.2.2 *Relationship to Study INTERVENTION*

Attribution/Assessment of Causality is a determination that describes the relationship or association of the study product with an adverse event.

This assessment of causality or relationship of AEs to the study product is provided by the Investigator and is determined by 1) temporal relationship of the event to the administration of study product, 2) whether an alternative etiology has been identified, and 3) biological plausibility. Causality must be assessed separately for each study product.

The causality assessment categories that will be used for this study are described below.

1. Causality assessments that are considered not related to study product:

a. Not related:

The event is related to an etiology other than the study product (the alternative etiology must be documented in the participant's medical record).

If an SAE is considered "unrelated" to study product, the Investigator should offer his/her clinical opinion as to what factor(s), agent(s), or process(s) were the likely causative mechanism for the event.

2. Causality assessments that are considered related to study product:

a. Possible:

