Changes in the severity of an AE will be documented to allow an assessment of the duration of the event at each level of severity to be performed. AEs characterized as intermittent require documentation of onset and duration of each episode.

The study research coordinator will record all reportable events with start dates occurring any time on or after the enrollment visit until 7 days (for non-serious AEs) or 30 days (for SAEs) after the last day of study participation. At each study visit, the research coordinator will inquire about the occurrence of AE/SAEs since the last visit. Vaccine-related and/or reportable events will be followed for outcome information until resolution or stabilization.

Clinical Laboratory Changes:

Safety laboratory assessments will be carried out locally at UNC and evaluated by the Investigator (or designee) to ensure participant safety. The Investigator (or designee) is responsible for reviewing the results of all laboratory tests as they become available.

- Laboratory values that fall outside of a clinically accepted reference range or differ significantly from previous values must be evaluated for clinical significance by the Investigator (or designee). The Investigator (or designee) may repeat the laboratory test or request additional tests to verify the results of the original laboratory tests.
- If the Investigator (or designee) determines the laboratory value is an abnormal change from baseline and is of clinical significance for that participant, it is considered an AE.
- Generally, Grade 1 and Grade 2 laboratory findings need not be reported as AEs unless deemed clinically significant by the Investigator (or designee).
- Consistent with the DAIDS designation of Grade 3 events as severe or medically significant and Grade 4 events as life-threatening, Grade 3 and Grade 4 laboratory findings should be reported as AEs or SAEs, as appropriate.
- The test result or finding should be reported as the AE. Such laboratory values should generally be recorded as “increased” or “decreased” (e.g., change from baseline potassium of 5.0 to 3.5 mEq/L = potassium decreased).

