10.1.2 Study Discontinuation and Closure

This study may be temporarily suspended or prematurely terminated if there is sufficient reasonable cause. Written notification, documenting the reason for study suspension or termination, will be provided by the suspending or terminating party to study participants, funding agency (NIH), the FDA, the University of Oxford, and the UNC IRB. If the study is prematurely terminated or suspended, the study PI (or designee) will promptly inform study participants, the UNC IRB, and DAIDS and will provide the reason(s) for the termination or suspension. Study participants will be contacted, as applicable, and be informed of changes to the study visit schedule.

Circumstances that may warrant termination or suspension include but are not limited to:

- Determination of unexpected, significant, or unacceptable risk to participants
- Demonstration of efficacy that would warrant stopping
- Insufficient compliance to protocol requirements
- Data that are not sufficiently complete and/or evaluable
- Determination that the primary endpoint has been met
- Determination of futility

Study may resume once concerns about safety, protocol compliance, and data quality are addressed, and satisfy the sponsor, the UNC IRB, DAIDS, and/or the Food and Drug Administration (FDA).

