10.1.6 Safety Oversight

Safety oversight will be under the direction of a Safety Monitoring Committee (SMC) composed of individuals with the appropriate expertise. Members of the SMC are independent from the study conduct and free of conflict of interest.

The SMC advises the study PI and protocol team for this First in Man, Phase I study. The primary responsibility of the SMC is to monitor human subject safety. The SMC considers study-specific data as well as relevant background information about the disease, test agents, and target population under study.

During the trial, the SMC will review:

- Real-time and cumulative safety data for evidence of study-related adverse events;
- Adherence to the protocol;
- Factors that might affect the study outcome or compromise the trial data (such as protocol violations, losses to follow-up, etc.).
- Review the achievement of enrollment benchmarks

The SMC will receive monthly reports via email for review and comments. The SMC will be contacted directly via email (and possibly via teleconferencing) for any event or situation that impacts participant safety throughout the study and specified interventions or study participation will be suspended or terminated dependent on the response of the SMC.

The study will undergo review at least annually by the SMC. The SMC will review information on accrual, baseline characteristics, conduct of the study (including premature study discontinuations and premature study treatment discontinuations), AEs by treatment arm (including protocol team assessment of relationship to study treatment), virologic failures, and HIV-1 RNA levels over time, and completeness of follow-up.

Safety Pause

Enrollment into the study and treatment injections will be temporarily suspended and the Study Monitoring Committee (SMC), unblinded to treatment assignment, will be asked to review all safety data. Review will include the relation to study treatment of the event(s) thought by the blinded core team to be a primary safety outcome, if any of the following occur:

- a) Two or more participants experience a primary safety outcome measure that is a Grade ≥ 3 AE possibly related to study treatment (as judged by the core team, blinded to treatment arm); or
- b) One or more participants experience an SAE possibly related to study treatment (as judged by the core team, blinded to treatment arm).

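### The Grade 4 discontinuation sentence in section 8.3.4 has no stated scope, and one related Grade 4 event not classed as serious brings no automatic hold on dosing

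*Combined protocol and SAP*

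**What the plan says.** Under Grade 4 Toxicity, section 8.3.4 requires that the protocol team and the SMC be told within 24 hours of a Grade 4 event judged at least possibly related. It then adds: "All study treatments will be discontinued in the event of Grade 4 AEs possibly related to study treatment". The sentence names neither a participant nor the trial.

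Section 7.1 states: "There is only one study treatment intervention visit at Day 0". Section 6.1.2 likewise gives every participant one administration.

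The trial-level rules are in sections 9.2.1 and 10.1.6. Both have two triggers. The first is two participants with a related event of Grade 3 or higher. The second, in the wording of 10.1.6, is "One or more participants experience an SAE possibly related to study treatment (as judged by the core team, blinded to treatment arm". Under 10.1.6 the consequence is a temporary suspension of enrollment and injections, an unblinded SMC review and an SMC recommendation on how to proceed. Neither section lists a single Grade 4 event.

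Section 10.1.2 adds a discretionary power: "This study may be temporarily suspended or prematurely terminated if there is sufficient reasonable cause".

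**The concern.** A site needs to know what happens to the next scheduled injections when one participant has a possibly related Grade 4 event. The sentence in 8.3.4 sounds like the firmest instruction in that section, yet in a one-injection trial it either does nothing or does something that the safety pause does not provide for. Section 10.1.6 describes the trial as first in man for these products, and its listed triggers hold dosing automatically. Whether a lone Grade 4 event holds dosing depends on how 8.3.4 is read and on whether the event is called serious.

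The stake is limited. Section 2.2.3 relies on extensive clinical experience with similar MVA vectors, and section 2.2.4 reports no possibly or likely related SAE in 213 recipients of the first-generation vaccine.

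**Working it through.** The plan states no figure for this rule, so there is none to reproduce. The check compares the provisions and then sizes the gap under stated assumptions.

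**Provisions side by side**

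| Section | Trigger | Level | Consequence |
|---|---|---|---|
| 8.3.4 | One possibly related Grade 4 event | Not stated; neighboring sentences concern participants | Treatment discontinued; team and SMC told within 24 hours |
| 9.2.1 | Two participants with related Grade 3 or higher, or one with a possibly related SAE | Trial | Enrollment suspended |
| 10.1.6 | The same two triggers | Trial | Temporary suspension of enrollment and injections, SMC review |
| 10.1.2 | Reasonable cause | Trial | Discretionary suspension or termination |

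**One possibly related Grade 4 event, case by case**

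1. *8.3.4 read for the participant.* Doses remaining = 1 planned − 1 given = 0. The sentence has no effect and does not disagree with 10.1.6. Dosing of others is held automatically only if the event is an SAE.
2. *8.3.4 read trial-wide, event classed as an SAE.* Both rules act, but one discontinues and the other suspends temporarily.
3. *8.3.4 read trial-wide, event not classed as an SAE.* 8.3.4 stops dosing; 9.2.1 and 10.1.6 do nothing unless another participant has a related Grade 3 or higher event.

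**Can a Grade 4 event be non-serious here?** Mostly not, but sometimes. The SAE definition in 8.3.1 includes "a life-threatening adverse event". Table 12 in 8.3.2.1 sets Grade 4 lower, at "Potentially life-threatening symptoms causing inability to perform basic self-care functions". The laboratory paragraph of 8.3.3 describes "Grade 4 events as life-threatening, Grade 3 and Grade 4 laboratory findings should be reported as AEs or SAEs, as appropriate", which leaves seriousness open for laboratory values. Blood counts and safety chemistries are drawn after dosing, so such a finding could arise. Table 3 lists a "Grade 4 CPK elevation" in an earlier MVA study of 20 participants. It was counted there as an SAE, and CPK is not among this trial's safety chemistries, so it only illustrates the kind of event where the seriousness call would decide.

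**Exposure while the SMC reviews.** Participants dosed = weekly cap × weeks of review; the review time of 1 to 2 weeks is assumed.

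- Cap of 2 per week (6.1.2): 2 × 1 = 2 to 2 × 2 = 4. Expected on vaccine: 2 × 21/24 = 1.75 to 4 × 21/24 = 3.5.
- Cap of 1 per week (9.2.1.2): 1 × 1 = 1 to 1 × 2 = 2.

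**How often a Grade 4 trigger would fire.** The documents give no rate for related non-serious Grade 4 events, so r is assumed. With 7 + 7 + 7 = 21 vaccinees, P(at least one) = 1 − (1 − r)^21:

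- r = 0.5%: 1 − 0.995^21 = 0.0999
- r = 1%: 1 − 0.99^21 = 0.1903
- r = 2%: 1 − 0.98^21 = 0.3457

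Some of these events would pause the trial anyway, because another participant already had a related Grade 3 or higher event. The chance that exactly one such Grade 4 event occurs, with no related Grade 3 event in any vaccinee, is 21 × r × (1 − r − g)^20, where g is the assumed related Grade 3 rate:

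| r | g = 0 | g = 2% | g = 5% |
|---|---|---|---|
| 1% | 0.1718 | 0.1142 | 0.0609 |
| 2% | 0.2804 | 0.1856 | 0.0984 |

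Placebo recipients can also contribute, since relatedness is judged blind. If all 24 participants had the same rate, P(at least one) would be 0.2143 at 1% and 0.3842 at 2%.

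**The case against.** The strongest reply is that there is no conflict. The Grade 4 paragraph is written about participants. Section 8.3.8 uses the same discontinuation wording for pregnant women although no second dose exists, and for trial-level action the protocol speaks of suspending or terminating. On that view the sentence is harmless repeat-dose wording. This stands. A reader might infer that 8.3.4 flatly contradicts 9.2.1 and 10.1.6, but the documents support only a conditional difference, on the less natural reading. Nor can both harms occur together: read trial-wide there is no gap in protection, and read for the participant there is no contradiction.

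A second reply is that the SMC is already involved. It is told within 24 hours, and apart from the listed triggers 10.1.6 says it will be contacted about anything affecting participant safety, with interventions suspended or terminated according to its response. The SAE definition also admits important medical events on the judgment of investigator or sponsor, so a worrying laboratory value can be called serious and pause the trial. This also stands, and it rules out the inference that a related Grade 4 event would go unattended. These routes need someone to decide, however, whereas the listed triggers hold dosing while the decision is made.

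A third reply is that a new trigger could halt the trial for one unconfirmed, asymptomatic laboratory value, and that the non-hematologic dose-limiting definition in 8.3.4 requires confirmed, symptomatic events. This is fair, and the fix requires confirmation on repeat.

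**Conclusion.** The point holds in a narrow form and is minor. The sentence in 8.3.4 lacks a scope. On its more natural reading it does nothing, and only on a trial-wide reading does it differ from the safety pause, in both trigger and consequence. What remains in practice is one situation: a single possibly related Grade 4 event not classed as serious, for which no automatic hold applies while the SMC considers it. The documents contain no example of such an event with these vaccines.

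The two-to-four-participant exposure rests on an assumed review time of one to two weeks and on dosing at the 6.1.2 cap. The pause frequencies rest wholly on assumed event rates.

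**What to change.** Make three wording changes.

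- In 10.1.6, add limb (c): any participant has a Grade 4 adverse event, confirmed on repeat if it is a laboratory value, that the blinded core team considers at least possibly related to treatment. The temporary suspension and SMC review are the same as for (a) and (b).
- In 8.3.4, replace the discontinuation sentence with a pointer to limb (c).
- In 9.2.1, list (c) in the summary of suspension triggers.

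The cost is an occasional extra temporary pause. At an assumed rate of 0.5% to 2%, the chance of at least one such event among 21 vaccinees is about 10% to 35%. That is an upper figure for extra pauses due to vaccinees, because some would coincide with limb (a); placebo events judged related under blinding would add to it. If the sponsor does not want a new trigger, the minimum is to state the scope of the 8.3.4 sentence or delete it. That cures the wording but leaves the hold to discretion.
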